## **8.3 Primary Effectiveness Outcome Analyses Variables**

The analysis of the primary objective of the study will be performed in the per protocol set with available data pertaining to the study primary endpoint, i.e. baseline and 12-month VA data.

The mean change in VA from baseline to month 12 along with the 95% confidence interval (CI) will be calculated for subjects completing 12 months of follow-up. Paired sample t test will be applied to compare the 12-month VA to Baseline VA.

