### CONFIDENTIAL

This document is confidential and the property of individual. No part of it may be transmitted, reproduced, published, or used by other persons without prior written authorization from the author.

overall much less favorable than what was achieved in the pivotal ranibizumab studies with fixed monthly follow-ups and monthly intravitreal injections or injections as needed based on protocol's strict guidelines. In this study, treatment outcomes were likely to be affected by deficiencies in regular monitoring and by the insufficient implementation of optimal diagnostic and retreatment criteria. (30)

In Greece there is limited data of the effect and safety of individualized treatment of patients with neovascular AMD with ranibizumab in routine clinical practice. Consequently, this 1-year observational multicenter study attempts to collect data on the effectiveness and safety of individualized treatment with ranibizumab in everyday clinical practice in a representative sample of Greek patients with treatment naive neovascular AMD. The study also aims to evaluate treatment patterns of ranibizumab administration in these patients treated outside the highly standardized phase III clinical trials.

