## **2 Study Objectives**

The main objectives of this observational cohort study are to evaluate effectiveness of ranibizumab and also to evaluate safety and to describe follow-up as well as treatment patterns in treatment naive patients with neovascular AMD in routine clinical practice in Greece for the total study population.

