### **2.1 Primary Objective**

- To evaluate the functional effectiveness of ranibizumab treatment in treatment naive patients with neovascular AMD in routine clinical practice in Greece as assessed by mean change in VA from baseline to month 12.

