## **8.1 Analysis sets**

The enrolled set will include all patients having signed the informed consent, and with at least a baseline assessment.

The Per Protocol Set will consist of all patients who complete the study without any major protocol deviations.

The study eye set will include all study eyes treated with ranibizumab.

In accordance to the non-interventional design of the study, all statistical analyses with the exception of the primary objective will be performed in all eligible subjects with available data who have been enrolled into the study, regardless of whether or not they have finally completed their projected participation in the study.

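### The primary VA analysis is confined to per-protocol completers, although the study's aim is effectiveness in routine practice

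*Protocol*

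**What the plan says.** Three filters apply to the primary analysis.

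- **Completion and no major deviation.** Section 8.1: "The Per Protocol Set will consist of all patients who complete the study without any major protocol deviations".
- **Both VA values.** Section 8.3: the primary analysis "will be performed in the per protocol set with available data pertaining to the study primary endpoint", meaning VA at baseline and at 12 months.
- **Completion again.** Section 8.3: the mean change and its 95% CI "will be calculated for subjects completing 12 months of follow-up".

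The restriction is deliberate and applies to one objective only. Section 8.1 appeals to the non-interventional design and states that "all statistical analyses with the exception of the primary objective will be performed in all eligible subjects with available data who have been enrolled", whether or not they completed. No reason is given for the exception.

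The primary objective in section 2.1 is "To evaluate the functional effectiveness of ranibizumab treatment in treatment naive patients with neovascular AMD in routine clinical practice in Greece". Section 4.3 requires consecutive enrolment so as to avoid selection bias. Section 8.4.3 analyses the 12-month CRT change in the enrolled set, with last observation carried forward where data are missing. The Data analysis part of the synopsis gives the paired comparison for VA but names no analysis set.

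**The concern.** Section 1.2 separates efficacy under ideal conditions from effectiveness in everyday care and says that real-life results have been worse than trial results. A per-protocol completer analysis moves the estimate back towards the first question. Patients who leave, are lost, or deviate in a major way are part of routine practice, and their results are removed from the main effectiveness figure. Consecutive enrolment guards against selection at entry, but it cannot protect against selection applied afterwards.

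Two things are at stake. First, if excluded patients fare differently from those included, the reported mean change does not estimate the mean for the enrolled cohort, and neither the paired CI nor a larger sample corrects this. Second, the functional and anatomic 12-month results would come from different sets of patients and could not be read side by side.

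**Working it through.** **The plan's own figure (section 8.5).** Inputs: SD of change 15.4 letters, half-width 2 letters, 95% CI, dropout 10%.

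- n = (1.96 × 15.4 / 2)² = 227.8, so 228. This agrees with the plan.
- 228 × 1.10 = 250.8, so 251. This agrees with the plan.

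**Precision by number analysed.** Half-width = 1.96 × 15.4 / √n.

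- All 251 contributing: 1.91 letters.
- 10% lost (251 × 0.90 = 225.9, so 226): 2.01 letters.
- 20% lost (251 × 0.80 = 200.8, so 201): 2.13 letters.

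The loss of nominal precision is small. The issue is whom the interval describes.

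**Bias from exclusion.** Let f be the share excluded and D the mean change in included patients minus that in excluded patients. The cohort mean is (1 − f) × included mean + f × excluded mean, so

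bias = included mean − cohort mean = f × D.

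The protocol gives neither f nor D. The only loss figure is the 10% dropout in section 8.5, used here as an assumed f. It makes no separate allowance for major deviations or for a missing baseline VA. The values of D are assumptions throughout.

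**Coverage of the cohort mean by the nominal 95% CI.** With SE = 15.4/√n and b the bias, coverage = Φ(1.96 − b/SE) − Φ(−1.96 − b/SE).

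| f (assumed) | D, letters (assumed) | b = f × D | n | SE | b/SE | Coverage |
|---|---|---|---|---|---|---|
| 10% | 0 | 0 | 226 | 1.02 | 0 | 95% |
| 10% | 5 | 0.5 | 226 | 1.02 | 0.49 | about 92% |
| 10% | 10 | 1.0 | 226 | 1.02 | 0.98 | about 84% |
| 20% | 5 | 1.0 | 201 | 1.09 | 0.92 | about 85% |
| 20% | 10 | 2.0 | 201 | 1.09 | 1.84 | about 55% |

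A negative D (excluded patients doing better) gives a bias of the same size in the other direction.

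**The case against.** **The direction is not documented.** A reader might infer that the included patients are shown to be a favourable selection. They are not. Section 1.2 says of the cited German non-interventional study that "treatment outcomes were likely to be affected by deficiencies in regular monitoring", but that concerns the cohort as a whole and not those who left it. Sections 4.4 and 4.4.1 allow withdrawal for any reason. An upward bias is plausible, but it is an inference.

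**The three-visit rule removes few patients by itself.** A reader might infer that sparsely monitored patients are largely screened out. Section 4.4 counts the baseline and end-of-study visits towards the three, and section 5.2 asks for only one visit in between. A patient seen at both ends fails the rule only if there was no intermediate visit at all. Major deviation is not defined in the protocol, so the number removed on that ground is unknown.

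**Interim VA may be thin.** Table 5-1 is a recommended schedule, reporting every visit is only recommended (section 5.2), baseline VA is only recommended (section 5.1.5), and there is no withdrawal visit (section 5.4). An early leaver may contribute little beyond baseline.

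**A severe loss of coverage is one scenario.** A reader might take the 55% as the expected result. It needs 20% excluded and a 10-letter gap, and neither figure comes from the protocol.

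**The population phrase is weak evidence.** Section 2 ends its list of aims with "in routine clinical practice in Greece for the total study population". This may mean overall rather than by subgroup, and section 2.1 does not repeat it. The argument does not depend on it.

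**Design and disclosure.** The study has one arm, section 8 says it is not meant to confirm or reject hypotheses, and the restriction is openly stated. The SAP, which is not shown, might add a VA analysis in a wider set.

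All of this limits how strongly the size and direction can be put. It does not remove the mismatch: the primary set is fixed in the protocol itself, against the principle that section 8.1 states for every other analysis.

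**Conclusion.** The point holds as a mismatch between the primary analysis set and the aim. Sections 8.1 and 8.3 fix the main effectiveness estimate to completers without major deviations who have both VA values, in a study of routine-practice effectiveness whose own principle is to analyse all eligible enrolled patients. VA and CRT would be reported for different populations.

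The resulting bias is possible and plausibly upward, but its direction and size cannot be derived from the protocol. With 10% excluded and a gap of 5 to 10 letters, both assumed, it is 0.5 to 1.0 letter. It equals the planned 2-letter margin only under stronger assumptions, such as 20% and 10 letters, and it is zero if excluded patients do as well as the rest. Confidence is high about the restriction and much lower about its numerical effect.

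**What to change.** In sections 8.1 and 8.3, and in the Data analysis part of the synopsis:

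1. Define the primary set as all treated study eyes with a baseline VA, regardless of completion or deviations. Section 8.1 already defines a study eye set of treated eyes that could serve as the base; no effectiveness analysis names it at present.
2. Estimate the Month-12 mean change and its 95% CI from all recorded VA values, by a mixed model with visit windows or continuous time, or by multiple imputation.
3. Add a sensitivity analysis for data not missing at random, for example shifting the unobserved Month-12 values by a range of letters.
4. Keep the per-protocol paired analysis as supportive.

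**Cost.** No new visits or data are needed, and the planned 251 need not rise on this account: if all contributed at SD 15.4, the half-width would be 1.91 letters, although missing Month-12 values would widen it somewhat. Programming is modestly heavier because visits are unscheduled, and their timing may itself carry information about outcome. The estimate will rest on a stated missing-data assumption and may prove slightly less favourable or less precise. A protocol amendment is required under section 11.1.

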## **8.4 Analysis of secondary variables**

### **8.4.1 Safety variables**

Non-ocular adverse events by patient and ocular adverse events by study eye will be evaluated. The number and proportion of patients experiencing any serious AE and the number and proportion of patients experiencing any non-serious AE will be calculated and presented in frequency tables.

Frequency tables will be presented for AEs by causality, seriousness, discontinuation of therapy, action taken and outcome.

The safety objective will be interpreted with respect to the related number of treatments.

### **8.4.2 Treatment pattern variables**

The treatment pattern variables will be evaluated using summary statistics applied on the enrolled set.

The number of ranibizumab injections administered overall during treatment period, the number of visits and the average time interval (in weeks) between consecutive visits and injections will be summarized for the treated eye.

The reasons for the decision to treat or not (i.e. VA deterioration, OCT abnormality etc) will also be summarized in each visit. Reasons for treatment termination will be also evaluated.

Any topical use of antimicrobial agents pre- or post-injection will be evaluated.

### **8.4.3 Effectiveness variables**

Effectiveness of ranibizumab treatment will also be measured by mean change in CRT as an anatomic parameter. Statistical analyses will be performed in the enrolled set and will be based on observed data and, in case of missing data, Last Observation Carried Forward method.

The mean change in CRT, as indicated by OCT measurements, from baseline to month 12 along with the 95% CI will be calculated. Paired sample t test will be used to compare the 12-month CRT to Baseline CRT.

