## 1.2 Study Rationale

Real-life outcomes of ranibizumab treatment of neovascular AMD have consistently been found to be less favorable than clinical trial results (24-26). We have to distinguish between the *efficacy* and the *effectiveness* of an intervention. Efficacy trials are clinical trials that investigate whether an intervention produces the expected result under ideal circumstances. Effectiveness trials investigate whether a treatment results in the expected outcome under real, everyday routine clinical conditions and not under ideal circumstances (27).

Most of the times, the dosing regimens that are used in everyday clinical practice do not follow the treatment protocols of the above-mentioned multicenter clinical trials and differ among specialists, even in the same department.

Except from the strict, monthly administration of ranibizumab, many, more flexible regimens have been used among retina specialists. They all target to similar visual gain with fewer injections compared to monthly treatment. The official Summary of Product Characteristics (SPC) for ranibizumab in Europe recommends monthly intravitreal injections continued until maximum VA is achieved (9). One popular choice is treatment as-needed [Pro re nata (PRN)] where the first three consecutive monthly intravitreal injections are followed by a monthly monitoring with a VA and OCT-guided retreatment. More precisely, as retreatment criteria could be applied a 5-letter loss in VA and fluid as detected by OCT, a >100 µm increase in central retinal thickness (CRT), a new-onset classic CNV, a new macular haemorrhage or persistent macular fluid detected by OCT (28). Treat-and-extend (TE) is another flexible treatment strategy aiming to reduce retreatment rate and patient's overall visits. After three initial monthly ranibizumab TE scheme continues with monthly injections until no CNV activity is detected (i.e. subretinal or intraretinal fluid, loss of >5 letters in VA, or persistent/recurrent retinal haemorrhage). Thereafter, the interval to the next visit and injection is extended stepwise by 2 weeks to a maximum of 12 weeks. When any CNV activity is noted, this interval is shortened by 2 weeks (29).

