#### **CONFIDENTIAL**

This document is confidential and the property of individual. No part of it may be transmitted, reproduced, published, or used by other persons without prior written authorization from the author.

A level of  $p < 0.05$  will be considered to be statistically significant.

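### Last observation carried forward is the only stated rule for missing Month-12 CRT, so the estimate can be biased in either direction and its confidence interval is modestly too narrow

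*Protocol*

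**What the plan says.** Protocol section 8.4.3 fixes the analysis of the secondary anatomic endpoint.

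- **Population:** "Statistical analyses will be performed in the enrolled set". Section 8.1 defines this set: "The enrolled set will include all patients having signed the informed consent, and with at least a baseline assessment".
- **Missing data:** the analysis is "based on observed data and, in case of missing data, Last Observation Carried Forward method". The protocol gives no other handling of missing CRT, no limit on the age of a carried value, and no rule on whether a baseline value may be carried.
- **Estimate and test:** "The mean change in CRT, as indicated by OCT measurements, from baseline to month 12 along with the 95% CI will be calculated", and "Paired sample t test will be used to compare the 12-month CRT to Baseline CRT".

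Other sections determine how often a Month-12 CRT will be missing and how old the last value may be.

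- Section 5.2 sets no visit schedule and requires only one visit between baseline and end of study.
- Section 5.1.6 recommends, but does not require, that CRT be recorded.
- Section 5.3 puts the end-of-study visit at 12 months ± 7 days.
- Section 5.4 provides no withdrawal visit.
- Section 5 discontinues patients seen fewer than three times a year.

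Section 8.3, by contrast, analyses visual acuity (VA) only in per-protocol patients with both baseline and 12-month values.

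**The concern.** LOCF assumes that CRT does not change after the last scan. The protocol's background gives reason to doubt this. Section 1.2 describes an as-needed regimen in which the "first three consecutive monthly intravitreal injections are followed by a monthly monitoring with a VA and OCT-guided retreatment", and it lists an increase in CRT of more than 100 µm among possible retreatment criteria. Thickness can evidently rise again after the initial injections, and a scan from that early phase is then a poor stand-in for Month 12.

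The opposite error is also possible. A patient with a baseline CRT and no later one belongs to the enrolled set, and carrying that baseline forward records a change of exactly zero.

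The rule is not confined to drop-outs. It also fills patients still in follow-up who have no scan in the 15-day end-of-study window.

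The anatomic objective is an estimate of mean change. What is at stake is whether that estimate and its CI describe Month 12, or a mixture of Month 12 and whatever time each patient was last scanned.

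**Working it through.** **Inputs from the protocol.** Planned enrolment is 251 with 10% dropout (section 8.5). That figure comes from the VA precision calculation and reproduces: (1.96 × 15.4 / 2)² = 227.8, rounded up to 228, and 228 × 1.10 = 250.8, rounded up to 251. The protocol gives no expected CRT change, no CRT standard deviation and no rate of missing CRT. All CRT values below are therefore assumptions, shown as ranges.

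**Bias.** Let d be the fraction with no Month-12 CRT, E the reduction at the last on-treatment scan, R the mean worsening from then to Month 12 in those patients, and s the share of them whose carried value is the baseline.

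- Mean carried change: −(1 − s)E
- Mean true change: −E + R
- Bias = d × [−(1 − s)E − (−E + R)] = d × (sE − R)

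A negative bias overstates the reduction and a positive bias understates it. The sign depends on whether s is below or above R/E, and the protocol fixes neither.

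With d = 0.10:

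- All carried values on-treatment (s = 0): R = 25, 50 or 100 µm gives a bias of −2.5, −5 or −10 µm.
- All carried values at baseline (s = 1) and R = 0: E = 50, 100 or 150 µm gives a bias of +5, +10 or +15 µm.
- Half and half (s = 0.5), with E = 100 and R = 50: 0.10 × (50 − 50) = 0.

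With d = 0.20 the non-zero figures double.

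**Simulation check.** The settings were 251 patients, 1,500 runs per case, E = 100 µm, SD of change 100 µm and correlation 0.6 between the two times. All but the 251 are assumed.

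| Missing | s | R (µm) | Bias (µm) | Coverage of 95% CI |
|---|---|---|---|---|
| 10% | 0 | 0 | 0.1 | 0.95 |
| 10% | 0 | 50 | −4.7 | 0.88 |
| 10% | 0 | 100 | −9.6 | 0.67 |
| 10% | 0.5 | 50 | −0.1 | 0.96 |
| 10% | 1 | 0 | +10.3 | 0.63 |

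**Width of the CI.** At equal SD, the LOCF interval uses 251 values and the observed-case interval uses 251(1 − d). The ratio of widths is √(1 − d):

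- 10% missing: √0.90 = 0.949, about 5% narrower
- 20% missing: √0.80 = 0.894, about 11% narrower
- 30% missing: √0.70 = 0.837, about 16% narrower

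The simulated half-widths agree: about 12.4 µm for LOCF against 13.1, 13.9 and 14.9 µm for observed cases. The first table row shows the limit of this point. When the no-change assumption is true on average, coverage is nominal. The severe coverage losses come from bias, not from the narrower interval.

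**Would a missing-at-random model remove the bias?** Take an assumed case: mean change is −100 µm at Month 3 and −80 µm at Month 12 in those who stay. Drop-outs leave after Month 3, resemble the others at that point, and drift to −30 µm.

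- 10% dropout: true mean 0.9(−80) + 0.1(−30) = −75. LOCF gives 0.9(−80) + 0.1(−100) = −82. A missing-at-random model targets −80.
- 20% dropout: true mean −70, LOCF −84, model −80.

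The model removes 2 of 7 µm and 4 of 14 µm. It improves on LOCF here but does not cure informative loss.

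**The case against.** Several objections have force.

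- **Overstated benefit.** A reader might infer that LOCF must exaggerate the anatomic benefit. The documents do not support that. Section 1.2 describes regimens and retreatment criteria; it does not say that CRT is lowest after the first injections or that it rises in those who leave. Baseline-only patients pull the estimate the other way, as does a scan taken at recurrence. A scan just outside the ±7-day window is almost a Month-12 value and does little harm.
- **Conflict with section 8.1.** A reader might see a contradiction, because that section says "all statistical analyses with the exception of the primary objective will be performed in all eligible subjects with available data who have been enrolled". But the same sentence covers patients who did not complete. Using their last available CRT fits that wording, and section 8.4.3 can be read as the specific rule.
- **Large coverage losses.** These can be produced at will by the choice of assumed values, so they illustrate the problem and do not predict its size.
- **Limited role of CRT.** It is a secondary endpoint, section 8 says the study is not meant to test pre-defined hypotheses, and it leaves full specifications to the SAP, which may contain sensitivity analyses.

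The last point lowers the weight of the matter but does not remove it. Section 8.4.3 makes an affirmative choice of main method; it is not a detail left open.

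**Conclusion.** The point holds in limited form. The protocol makes single imputation by LOCF the sole stated handling of missing Month-12 CRT, in a design where the last value can be months old or the baseline itself. The bias has unknown sign and size. At 10% missing it ranges from about −10 to +15 µm over the values tried, and errors in opposite directions may cancel. The interval is narrower than the measured Month-12 data alone support, by about 5% at 10% missing and 11% at 20%, assuming equal SDs.

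The bias figures rest wholly on assumed CRT values. The width ratios need only the missing fraction and the equal-SD assumption. The 10% is the protocol's dropout allowance; missing CRT could exceed it, given the narrow end-of-study window and optional recording. Consequences are limited to a secondary, descriptive endpoint, but the correction is cheap enough to be worth making.

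**What to change.** In section 8.4.3, replace LOCF as the main analysis with one of the following, applied to all observed CRT values in study eyes with a baseline CRT:

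- a longitudinal mixed model using actual time since baseline, or defined visit windows, because visits are irregular; or
- multiple imputation.

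Report the Month-12 mean change and 95% CI from that analysis. Keep the observed-case and LOCF results only as labelled sensitivity analyses, and state for LOCF whether a baseline value may be carried. Add one missing-not-at-random sensitivity analysis, for example a range of shifts towards baseline for patients who left, because the main analysis would assume missing at random.

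The cost is a wording change in the protocol and SAP, modest extra programming, a decision on how to model time, and a slightly wider CI. No new data or visits are needed.
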